7.1.2 Stage II

7.1.2.1 Evaluation Criteria for the Efficacy Endpoint

1. Percentage of patients reporting a clinical relapse of COVID-19 when assessed from day of discharge to 59 days after the day of randomization (Day 60).

Note: 'Clinical relapse' is defined as either the reappearance or worsening of severity (over the assessment on the day of discharge) of one or more of the above-mentioned COVID-19 associated symptoms, or the appearance of any of these symptoms (due to COVID-19 infection) for the first time after discharge.

2. Proportion of patients
 - a. With disease worsening and requires:
 - Admission to ICU
 - High flow nasal oxygen
 - Non-invasive mechanical ventilation
 - Invasive mechanical ventilation

AND

- b. Dying
- until Day 60 (regardless of whether patients are discharged from hospital before Day 28 or not)

7.2 Safety Evaluation Criteria

7.2.1 Stage I

1. Number (and percentage) of patients reporting treatment emergent adverse events (TEAEs) (by MedDRA system organ class and preferred term)

The AEs and SAEs occurring throughout the study will be collected irrespective of whether they are related to investigational product or not and will be presented as per the System Organ Class (SOC). The number of patients with treatment-emergent AEs will be collected and summarized based on the SOC and preferred term.

2. Changes of parameters at each assessment during the study/follow-up period, compared to baseline for:
 - Vital signs: body temperature, heart rate, respiratory rate, systolic/diastolic BP and oxygen saturation.
 - Clinical laboratory assessments: hematology, serum chemistry, urinalysis.
 - 12 Lead ECG: Changes in heart rate, PR, QRS, QT and QTcB intervals.

Vital signs will be measured at screening, at pre-dose only on Day 1 and at least twice, morning and afternoon, daily from Day 2 to Day 28 or discharge or discontinuation from the study. Laboratory assessments will be performed at screening, Day 4, Day 7, Day 10, Day 14, Day 21, and Day 28 or discharge or discontinuation. 12-Lead ECG will be performed at screening, Day 1

Study code: NV-05-983-2020
Protocol No.: CVD-04-CD-001
Sponsor name: [name], Limited
Clinical Study Protocol

(pre-dose), Day 4, Day 7, Day 10, Day 14, Day 21 and Day 28 or discharge (if discharge happens earlier than one or more of the above-mentioned assessment timepoints or study discontinuation (whichever is earlier). Pre-dose measurement will act as the baseline for vital signs, laboratory assessments and 12-Lead ECG parameters. The changes in these parameters will be compared between the treatment groups for each of these assessments.

7.2.2 Stage II

1. Number (and percentage) of patients reporting treatment emergent adverse events (TEAEs) (by MedDRA system organ class and preferred term)

The AEs and SAEs occurring throughout the study will be collected irrespective of whether they are related to investigational product or not and will be presented as per the System Organ Class (SOC). The number of patients with treatment-emergent AEs will be collected and summarized based on the SOC and preferred term.

Study code: NV-05-983-2020
Protocol No.: CVD-04-CD-001
Sponsor name: [name], Limited
Clinical Study Protocol

8 PHARMACOKINETIC/PHARMACODYNAMIC ASSESSMENTS

Not applicable.

Study code: NV-05-983-2020
Protocol No.: CVD-04-CD-001
Sponsor name: [name], Limited
Clinical Study Protocol

9 SAFETY ASSESSMENTS

9.1 Adverse Events

All clinical AEs occurring after the patient signs the Informed Consent Form and up to Day 60 or study discontinuation, whichever is earlier whether observed by the Investigator or reported by the patient, will be recorded on the AE electronic case report form (eCRF) page. All SAEs are to be reported according to the procedures in [Section 9.2](#) SAE Reporting-Procedure for Investigators. Pre-planned procedure or hospitalization for pre-existing conditions which do not worsen in severity should not be reported as SAEs (see [Section 9.1.1](#) for Definitions).

At each visit, the Investigator will determine whether any AEs have occurred by evaluating the patient. Adverse events may be directly observed, reported spontaneously by the patient or by questioning the patient at each study visit. Patients should be questioned in a general way, without asking about the occurrence of any specific symptoms. All laboratory values must be appraised by the Investigator as to clinical significance. All post-baseline abnormal laboratory values considered clinically significant by the Investigator must be recorded in the AE page of the eCRF.

Investigator should follow patients with AEs until the event has resolved or the condition has stabilized. In case of unresolved AEs including significant abnormal laboratory values at the end of study assessment, these events will be followed up until resolution or until they become clinically not relevant.

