3.1.6.1 Study Discontinuation

3.1.6.1.1 Study discontinuation criteria

When a patient meets any of the following criteria, the Principal Investigator or a Sub-Investigator will discontinue the patient from the study.

- a. The patient requests withdrawal from the clinical study
- b. The patient died
- c. The patient is lost to follow-up
- d. The patient is otherwise deemed ineligible to continue in the study by the Principal Investigator or a Sub-Investigator (e.g adverse event or pregnancy)
- e. Upon request by the CRO or Sponsor Medical Monitor (with appropriate justification)

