3.1.6.2.2 Study treatment discontinuation procedures

If the study drug administration is discontinued based on [Section 3.1.6.2.1](#), the Principal Investigator or a Sub-Investigator need to take appropriate action. The date of, and reasons for, discontinuing administration of the study drug and the details (including actions taken after discontinuation of drug administration and the outcome, if the study drug was discontinued due to an AE) are to be investigated and captured in the eCRF. One of applicable reason for discontinuation from the list below will be entered in the eCRF.

Even if the administration of study treatment is stopped, patients will be encouraged to continue in the study and provide the applicable scheduled assessments, as specified in [Section 6.3](#) until the patients are discharged, as long as they do not meet the criteria for study discontinuation.

Study code: NV-05-983-2020
 Protocol No.: CVD-04-CD-001
 Sponsor name: [name], Limited
 Clinical Study Protocol

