The study period during which AEs must be reported is defined as the period from the time patient signs the Informed Consent Form to Day 60 or study discontinuation, whichever is earlier. If follow up is required beyond Day 60 for safety related reasons, additional visit(s) may be scheduled for individual patients.

Medical History Condition

Study code: NV-05-983-2020
Protocol No.: CVD-04-CD-001
Sponsor name: [name], Limited
Clinical Study Protocol

A medical history condition is any clinically significant medical/surgical condition already present at the time of informed consent.

Pre-treatment Adverse Events

Any clinically significant abnormality between the time of informed consent and intake of the first dose of the study drug in the trial, which meets the definition of AE, should be recorded as a pre-treatment AE (or non-Treatment Emergent Adverse Event). Any new clinically significant event or worsening of existing medical history condition between the time of informed consent and intake of the first dose of the study drug in the trial, which meets the definition of AE will also be considered as pre-treatment AE.

Treatment Emergent Adverse Events

All AEs recorded after the first dose of study drug (on Day 1) until Day 30 or study discontinuation, whichever is earlier will be considered as Treatment Emergent Adverse Events (TEAEs). Disease signs, symptoms and/or laboratory abnormalities already existing prior to the use of the product will not be considered as adverse experiences after treatment (TEAEs) unless they reoccur after the patient has recovered from the pre-treatment condition or they represent an exacerbation in intensity or frequency, or the character of the condition worsens during the study period.

Post Treatment Adverse Events

All AEs recorded after Day 30 until Day 60 or study discontinuation, whichever is earlier will be considered as post treatment AEs.

Physical Examination Findings

At screening assessment, any clinically significant abnormality detected on physical examination should be recorded as a pre-existing condition. During the visits that fall within the treatment period and after the end of the study, any new clinically significant findings/abnormalities that meet the definition of an AE must be recorded and documented as an AE.

Abnormal Laboratory Values

A clinically significant laboratory abnormality should be documented as an AE if any one of the following conditions is met:

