 - 400 – Time-to-event analysis: use of a proportional hazards model or log-rank test should
 401 be supplemented by a display of Kaplan-Meier curves in each treatment group.
 - 402
 - 403 • To improve the precision of treatment effect estimation and inference, sponsors should
 404 consider adjusting for prespecified prognostic baseline covariates (e.g., age, baseline
 405 severity, comorbidities) in the primary efficacy analysis and should propose methods of

²⁷ See 21 CFR 312.32.

²⁸ See the guidance for industry *Safety Reporting Requirements for INDs and BA/BE Studies* (December 2012). In addition, FDA has proposed relevant recommendations in the draft guidance for industry *Safety Assessment for IND Safety Reporting*. When final, this guidance will represent the FDA's current thinking on this topic.

Contains Nonbinding Recommendations

- 406 covariate adjustment. For example, for a binary endpoint, methods can be used to gain
407 precision in the evaluation of the difference in proportions.²⁹
408
- 409 • If a treatment trial enrolls a mixture of patients with different baseline severity levels,
410 sponsors should conduct subgroup or interaction analyses by baseline severity to assess
411 for differential treatment effects.
412
 - 413 • The trial should aim to minimize missing data. The protocol should distinguish between
414 discontinuation from the study drug and withdrawal from study assessments. Sponsors
415 should encourage subjects who discontinue therapy to remain in the study and to continue
416 follow-up for key outcomes. Virtual follow-up is acceptable if appropriate, and the aim
417 should be to record vital status for all subjects.
418
 - 419 • For the primary analyses, death should not be considered a form of missing data or
420 censoring. Death should be incorporated into the endpoint as a highly unfavorable
421 possible outcome. For primary endpoints other than all-cause mortality, a treatment effect
422 could be driven by non-mortality components (e.g., hospitalization) despite increased
423 mortality on drug. Therefore, analyses of all-cause mortality will be important regardless
424 of the selected primary endpoint.
425

²⁹ Ge M, Durham LK, Meyer RD, Xie W, and Thomas N, 2011, Covariate-Adjusted Difference in Proportions from Clinical Trials Using Logistic Regression and Weighted Risk Differences, *Drug Inf J*, 45:481–493.

Contains Nonbinding Recommendations

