 - 2) The next lowest ranks will be given to patients who do not meet the definition of success but are lost to follow-up or are missing endpoint data for Day 28, but survive to Day 28, beginning with the earliest day for which data are lost for the rest of the study.
 - 3) The next lowest ranks will be given to patients who are informative withdrawals – i.e., they withdraw for a reason related to probable treatment failure – but survive to Day 28, beginning with the withdrawals closest to Day 28 (i.e., the latest withdrawals).
 - 4) The next lowest ranks will be given to patients who are followed to Day 28 but do not meet the primary endpoint definition, beginning with patients with the lowest clinical status score on Day 28.
 - 5) The highest (worst) ranks will be given to patients who die, beginning with the deaths closest to Day 28. Thus, the highest rank will be assigned to the first death.

This sensitivity analysis will be done using ITT population.

Listing will be provided for the 10-point ordinal scale of clinical status and oxygen saturation level.

10.6.2 Secondary Analysis:

All secondary analysis will be done using ITT population.

1. Time to discharge from hospital

Time to discharge from hospital = Date of discharge – Date of randomization +1

Statistical Analysis Plan
Sponsor: [name], Inc

Study Number: NV-05-983-2020

Version: 2.0 Date: 06JAN2021

Time to discharge in days will be summarized descriptively. Time to discharge will be compared between the treatment groups using the Cox proportional hazard model. The hazard ratio and its corresponding two-sided 95% confidence interval (CI) and two sided *p*-value at 5% level of significance will be obtained from the above Cox proportional hazard model; Also Median time, quartile, inter quartile range estimate will be presented.

Patients whose does not discharged up to Day 28 will be right censored as of day 28. Patients who discontinue the study for any reason – withdrawal because of an adverse event or worsening of symptoms, switch to rescue therapy, loss to follow-up, etc. – will be right censored at Day 28.

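### After study discontinuation the protocol plans no collection of new adverse events or vital status, so Day 28 and Day 60 survival can be unknown for patients taken off study

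*Protocol*

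**What the plan says.** Protocol 9.1 states what is recorded: "All clinical AEs occurring after the patient signs the Informed Consent Form and up to Day 60 or study discontinuation, whichever is earlier". The reporting-period paragraph under Protocol 9.1.1.2 repeats this as "the period from the time patient signs the Informed Consent Form to Day 60 or study discontinuation, whichever is earlier". The definitions of treatment-emergent events (to Day 30) and post-treatment events (Day 30 to Day 60), under the same heading, carry the same early stop.

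Protocol 3.1.6.1.1 lists reasons for leaving the study. Criterion (d) reads "The patient is otherwise deemed ineligible to continue in the study by the Principal Investigator or a Sub-Investigator (e.g adverse event or pregnancy". Protocol 9.3 also takes a patient who becomes pregnant off the study.

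Stopping the drug is a separate matter. Protocol 3.1.6.2.1 lists adverse events among the reasons for stopping the drug, and under 3.1.6.2.2 "patients will be encouraged to continue in the study and provide the applicable scheduled assessments". That encouragement runs until hospital discharge, and only while no study-discontinuation criterion is met.

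When a patient leaves the study, Protocol 3.1.6.1.2 and 4.2.1 call for the Day 28 set of assessments. The heading of 6.3.1.5 places that set at discontinuation if it comes before Day 28.

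The regulatory guidance reproduced in Protocol Appendix I, part E, says of follow-up that the aim "should be to record vital status for all subjects".

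**The concern.** The window for new safety data closes at an event that treatment itself may cause. If a patient is taken off study for an adverse event and later has an unrelated serious event or dies, no visit, call or vital-status check is specified that would find it.

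Several analyses rely on that information:

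- **Worst-rank sensitivity analysis (SAP 10.6.1).** Category 2 (lost or missing) and category 3 (informative withdrawals, where "they withdraw for a reason related to probable treatment failure") each require that the patient survived to Day 28. Category 5 requires the deaths. The SAP has no rule for unknown survival.
- **Primary endpoint, part (c).** It requires survival without COVID-19 readmission through Day 28. A patient who reached a score of 4 or lower and then left the study has no planned source for (c), and the SAP does not say whether that patient counts as an event or is censored.
- **Mortality (SAP 10.6.2, item 15 and Stage II item 2).** The Day 28 endpoint stops at discharge, so it is exposed for patients taken off study while still in hospital. The Day 60 endpoint runs regardless of discharge, so it is exposed for every discontinued patient.

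If withdrawals for adverse events are more frequent in one arm, later serious events and deaths are undercounted there, and a death after exit may be ranked as a surviving withdrawal.

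**Working it through.** **1. The plan's own sample size (Protocol 11.10).** Inputs: hazard ratio 1.25, two-sided alpha 0.05, power 80%, event probabilities 0.9 and 0.8 (mean 0.85), 1:1 allocation, 5% dropout.

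- Schoenfeld: events = 4(1.960 + 0.842)² / (ln 1.25)² = 631, as stated.
- Patients: 631 / 0.85 = 742.4, or 371 per arm, as stated.
- Dropout: 371 × 1.05 = 389.6, rounded up to 390, as stated. Dividing by 0.95 gives 390.5, or 391. The difference is immaterial.

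No figure is in dispute, and closing the gap does not change the sample size.

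**2. What is and is not collected after study discontinuation.**

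| Information | Planned after exit? | Where |
|---|---|---|
| Course of an event open at exit | Yes, to resolution or stabilisation | Protocol 4.2.1, 9.1, 9.2 |
| Death caused or significantly contributed to by an open event | Yes, as a fatal outcome | Protocol 9.1.1.6 |
| Event with onset after exit | No, outside the window | Protocol 9.1, 9.1.1.2 |
| Death not linked to an open event | No | No section provides it |
| Clinical status at calendar Day 28 | No, done at exit if earlier | Protocol 6.3.1.5 |
| Enquiry after missed visits | Conditional on cooperation; no visits are specified after exit | Protocol 3.1.6.1.2 |

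**3. Observation lost per patient.** Discontinuation on Day 10, as an example:

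- Adverse-event window: 60 − 10 = 50 days.
- Time to Day 28: 28 − 10 = 18 days.

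**4. Number of patients.** At the stated 5% dropout, 0.05 × 780 = 39 patients, or 19.5 per arm. This is an upper bound at that rate, because it counts every dropout as a patient with unknown Day 28 status.

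**5. Deaths at risk of not being collected.** The documents give neither the share of dropouts due to adverse events nor the mortality among them. Assumed ranges are 25–100% and 5–30%.

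- Low: 39 × 0.25 × 0.05 = 0.5.
- Middle: 39 × 0.50 × 0.15 = 2.9.
- High: 39 × 1.00 × 0.30 = 11.7.

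Deaths captured through open events must be subtracted from each. The figures scale with dropout. At 2.5% there are 19.5 patients and at most 5.8 deaths; at 10% there are 78 patients and at most 23.4 deaths.

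**The case against.** The strongest reply is that the protocol already separates stopping the drug from leaving the study, and that adverse events normally lead only to the first. Protocol 3.1.6.2.1 covers adverse events in general, related serious events, and Grade 3 uric acid or transaminase values. All of these stop the drug, and the patient is then encouraged to remain, with the window still open. Criterion (d) of 3.1.6.1.1 is discretionary, with an adverse event given only as an example. A patient who does leave for an adverse event usually has that event open, so it is followed and a resulting death is recorded.

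All of this stands, and it limits the point. It does not supply a source for events that start after exit or for deaths unrelated to an open event.

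Two stronger readings are tempting, and the documents do not support them:

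- **That every patient harmed by the drug drops out of safety follow-up.** A hepatic event, for instance, falls under the drug-stopping rules, and a later seizure or death would be collected unless the investigator separately took the patient off study.
- **That the worst-rank analysis cannot be carried out.** Categories 1 and 4 can be assigned wherever follow-up to Day 28 is complete, and observed deaths go to category 5. Only affected patients' placement is uncertain, chiefly category 2 or 3 against 5. For patients truly lost to follow-up, the loss itself is a cause as well.

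It is also fair to say that worst-rank is a sensitivity analysis. In the primary analysis, deaths and discontinuations for treatment-related adverse events are both censored at Day 28. For a patient discontinued on that ground before reaching a score of 4 or lower, a later death therefore changes nothing. That reply does not cover patients who had already reached the score. Nor does it cover patients censored at exit for reasons classed as independent of study medication, whose later death would move their censoring to Day 28.

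**Conclusion.** The gap is real but bounded. New-onset adverse events after study discontinuation, and deaths not linked to an event open at exit, have no planned collection. Day 28 and Day 60 survival can therefore be unknown for patients taken off study.

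At the planned dropout this concerns at most about 39 of 780 patients. About 0.5 to 12 deaths are at risk, on assumed ranges for the adverse-event share and mortality, before subtracting those captured through open events.

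Any bias favours the arm with more adverse-event withdrawals, and arises only if withdrawals differ by arm. The documents give no basis for predicting such a difference, so the direction is conditional. The point still merits correction, because missing vital status cannot be recovered in the analysis.

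**What to change.** - **Collection window.** In Protocol 9.1 and in the reporting-period, treatment-emergent and post-treatment definitions under 9.1.1.2, replace the study-discontinuation cut-off. Collection should end early only for death, withdrawal of consent to follow-up, or loss to follow-up. The Day 30 and Day 60 limits stay.
- **Contacts.** For every discontinued patient who has not withdrawn consent to follow-up, use the existing Day 14, 21, 28, 42 and 60 calls to collect new adverse events, serious adverse events and vital status, and COVID-19 readmission through Day 28. Protocol 6.3.1.6 and 6.3.2 do not list vital status or readmission among the items for these calls, so they need adding.
- **Reconciliation.** Protocol 3.1.6.1.1(d), 3.1.6.1.2, 3.1.6.2.1, 3.1.6.2.2, 4.2.1, 6.3.1.5 and 9.3 should be reconciled on who leaves the study rather than only the drug. Which rule applies is for the sponsor and investigators to decide, and the data-collection change does not depend on it.

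The cost is protocol wording and a few more telephone calls.

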9.1.1 Definitions

9.1.1.1 Adverse Event (AE)

Any untoward medical occurrence in a patient or clinical investigation subject administered a pharmaceutical product and which does not necessarily have to have a causal relationship with this treatment.

An AE is therefore any unfavorable and unintended sign (an abnormal ophthalmic finding, for example), symptom (including physical, psychological or behavioral effect), or disease temporally associated with the use of a medicinal (investigational or marketed) product, experienced by a patient during their participation in an investigational study, in conjunction with the use of the drug or biologic, whether or not considered product-related.

This includes any untoward signs, symptoms, illness or clinically significant laboratory test abnormality that has appeared or worsened during the course of the clinical trial, experienced by the patient from the time of signing the informed consent until completion of the study. Throughout the patient's participation in the study, any new clinically significant findings/abnormalities that meet the definition of an AE must be recorded and documented as an AE.

9.1.1.2 Serious Adverse Event (SAE)

A serious adverse event is defined as any untoward medical occurrence that at any dose:

- Results in death,

Study code: NV-05-983-2020
 Protocol No.: CVD-04-CD-001
 Sponsor name: [name], Limited
 Clinical Study Protocol

- Is life-threatening,
- Requires inpatient hospitalization or prolongation of existing hospitalization,
- Results in persistent or significant disability/incapacity,
- Is a congenital anomaly/birth defect, or
- Is an important medical event.

Note: *The term “life-threatening” in the definition of “serious” refers to an event in which the patient was at risk of death at the time of the event; it does not refer to an event which hypothetically might have caused death if it were more severe.*

Medical and scientific judgment should be exercised in deciding whether expedited reporting is appropriate in other situation, such as important medical events that may not be immediately life-threatening or result in death or hospitalization but may jeopardize the patient's safety or may require intervention to prevent one of the other outcomes listed in the definition above. Examples include allergic bronchospasm, convulsions, and blood dyscrasias or development of drug dependency or drug abuse.

Note:

- *A procedure is not an AE or SAE, but the reason for the procedure may be an AE.*
- *Pre-planned surgeries or hospitalizations for pre-existing conditions which do not worsen in severity are not SAEs.*
- *Routine treatment or monitoring of the studied indication not associated with deterioration in condition should not be considered as SAE. For example, in the patient population for the current study, administration of supplemental oxygen should not in itself be considered as SAE, unless it is associated with a significant deterioration in subject's condition (such as development of ARDS and/or respiratory failure requiring invasive mechanical ventilation).*
- *. Hospitalization or prolongation of hospitalization for technical, practical, or social reasons, in absence of an AE should not be considered as SAE.*
- *Abnormal clinically significant laboratory values should not be reported as SAEs, unless they lead to prolongation of hospitalization on their own, while the underlying disease condition merited a discharge from the hospital.*

Adverse Event Reporting Period

The study period during which AEs must be reported is defined as the period from the time patient signs the Informed Consent Form to Day 60 or study discontinuation, whichever is earlier. If follow up is required beyond Day 60 for safety related reasons, additional visit(s) may be scheduled for individual patients.

Medical History Condition

Study code: NV-05-983-2020
Protocol No.: CVD-04-CD-001
Sponsor name: [name], Limited
Clinical Study Protocol

A medical history condition is any clinically significant medical/surgical condition already present at the time of informed consent.

Pre-treatment Adverse Events

Any clinically significant abnormality between the time of informed consent and intake of the first dose of the study drug in the trial, which meets the definition of AE, should be recorded as a pre-treatment AE (or non-Treatment Emergent Adverse Event). Any new clinically significant event or worsening of existing medical history condition between the time of informed consent and intake of the first dose of the study drug in the trial, which meets the definition of AE will also be considered as pre-treatment AE.

Treatment Emergent Adverse Events

All AEs recorded after the first dose of study drug (on Day 1) until Day 30 or study discontinuation, whichever is earlier will be considered as Treatment Emergent Adverse Events (TEAEs). Disease signs, symptoms and/or laboratory abnormalities already existing prior to the use of the product will not be considered as adverse experiences after treatment (TEAEs) unless they reoccur after the patient has recovered from the pre-treatment condition or they represent an exacerbation in intensity or frequency, or the character of the condition worsens during the study period.

Post Treatment Adverse Events

All AEs recorded after Day 30 until Day 60 or study discontinuation, whichever is earlier will be considered as post treatment AEs.

Physical Examination Findings

At screening assessment, any clinically significant abnormality detected on physical examination should be recorded as a pre-existing condition. During the visits that fall within the treatment period and after the end of the study, any new clinically significant findings/abnormalities that meet the definition of an AE must be recorded and documented as an AE.

Abnormal Laboratory Values

A clinically significant laboratory abnormality should be documented as an AE if any one of the following conditions is met:

- The laboratory abnormality is not otherwise refuted by a repeat test to confirm the abnormality
- The abnormality suggests a disease and/or organ toxicity, then the underlying condition should be captured as an AE.
- The abnormality is of a degree that requires active management; e.g. change of dose, discontinuation of the drug, more frequent follow-up assessments, further diagnostic investigation, etc.

Study code: NV-05-983-2020
 Protocol No.: CVD-04-CD-001
 Sponsor name: [name], Limited
 Clinical Study Protocol

Lab abnormalities found during the screening assessments will not be considered as AE but will be used by the Investigator in determining eligibility of the individual patient for study participation and included as part of the medical history.

Hospitalization, Prolonged Hospitalization or Surgery

Any AE that results in hospitalization or prolonged hospitalization should be documented and reported as a SAE. Any condition responsible for surgery should be documented as an AE if the condition meets the criteria for an AE.

Neither the condition, hospitalization, prolonged hospitalization, nor surgery are reported as an AE in the following circumstances:

- a) Hospitalization or prolonged hospitalization for diagnostic or elective surgical procedures for a pre-existing condition. Surgery should not be reported as an outcome of an AE if the purpose of the surgery was elective or diagnostic and the outcome was uneventful.
- b) Hospitalization or prolonged hospitalization required to allow efficacy measurement for the study.
- c) Hospitalization or prolonged hospitalization for therapy of the target disease of the study, unless it is a worsening or increase in frequency of hospital admissions as judged by the clinical Investigator.

